1. INTRODUCTION

Background

Medication errors are the leading cause of preventable harm in healthcare settings worldwide (1). An estimated 237 million medication errors occur in England alone every year, with 66 million considered clinically significant (2). There is an estimated cost to the NHS from definitely avoidable adverse drug reactions as a result of these errors of £98.5 million per year, consuming 181,626 bed-days and causing to 712 deaths(2).

Medication related clinical decision support systems, often integrated with electronic prescribing systems, are rapidly increasing in number over the last few decades, ranging from drug-drug interaction alerts to allergy checks and formulary support. A recent systematic review summarised that these systems are still relatively immature, with limited use of patient-specific input or human factors research used to develop them (3). There is an opportunity to improve these systems significantly for the benefit of the user and for patient safety. The World Health Organization propose that interventions to reduce medication error should include the development of technologies that are well understood and designed for the systems and practice they are applied to (1).

Human factors and usability engineering is an integral part of developing medical devices, such as clinical decision support (CDS) systems, to ensure that such devices are easy to use and can be used safely as intended (4). User testing / usability testing, which may incorporate several methods, should be conductive throughout the development process (at formative, summative assessment, and during post-market surveillance) (4). These methods are now becoming more common place in healthcare technology research and should continue to support the development of new technologies (4–7).

RxConnect

RxConnect, a newly registered UKCA marked medical device, is an on-demand clinical decision support tool that receives medication and patient inputs and uses them to filter an underlying formulary, such as the BNF, and perform dosing calculations, as needed, to return patient-specific dosing recommendations. RxConnect does not have a user interface and relies on an integration with third-party systems, such as electronic prescribing systems, to deliver CDS services to clinical end users. For this study a prototype user interface for RxConnect that emulates a typical electronic prescribing system will be used.

The study team hypothesise that use of RxConnect as a digital prescribing aid is quicker, easier, and as safe to use as currently available prescribing aids. This study aims to utilise user testing to prove or disprove the above hypothesis and to generate quantitative and

qualitative outputs to support the continued development of RxConnect prior to clinical deployment.

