2. STUDY OBJECTIVES

Primary objective

To determine whether the use of RxConnect as a prescribing aid, when compared with usual practice decreases or increases the number of prescribing errors

Secondary objectives

To determine whether the use of RxConnect as a prescribing aid, when compared with usual practice-

- 1. Decreases or increases the magnitude of dose errors
- 2. Decreases or increases the time to prescribe a medication
- 3. Decreases or increases the mental load as perceived by the prescriber
- 4. Alters the prescribing workflow

To explore the opinions of the participants regarding the use of RxConnect as a prescribing aid and indication-based prescribing more generally.

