3. STUDY DESIGN

Study Design

A mixed-methods cross-over observational study will be conducted to explore the safety, performance, and user perceptions of utilising RxConnect to support prescribing, in comparison to current practice.

Direct observation of participants will be conducted using multi-angle audio-visual recording, this will be set up behind the computer workstation, to capture the computer display and from above to capture the workstation. The cameras will not be angled to take footage of the participant face. A member of the research team will also be present through the study session.

Prescribing scenarios will be presented on laminated paper along with any relevant patient information, e.g. patient gender, age, weight, diagnosis, relevant medical history, relevant laboratory results.

Intervention arm: Prescribing with RxConnect via a prototype user interface

Participants will be asked to complete a number of practice prescribing tasks whilst *thinking aloud* to describe their thought process and actions. To undertake the prescribing tasks, participants will be asked to use the prototype user interface emulating an electronic prescribing front end, which presents RxConnect medication guidance to the clinical end user (the participant).

Once familiarised with the software workflow, the test prescribing tasks will be given to the participant. For these tasks the participants will be asked to perform the task without the need to think aloud. If the participant wishes to continue to think aloud so long as it doesn't distract

them from completing the task. The medication order the participants have generated using RxConnect support via the user interface will then auto populate a medication order form.

Control arm: Prescribing on Cerner with existing resources

Participants will be asked to perform similarly simple and then complex tasks using their usual practice methods when prescribing. Access will be provided to the prescribers usual electronic prescribing platform, including links to the British National Formulary, Medicines complete, local antimicrobial stewardship application, local intranet, and a generic online search engine. A hard copy of the BNF and BNFc will also be readily available.

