As with the intervention arm, if the participant wishes to continue to think aloud so long as it doesn't distract them from completing the task. Participants will be asked to enter their medication order for the patient within a 'test ward' on the Cerner Millennium Powerchart system.

Order of control vs intervention arm-

Each participant will be randomly assigned to begin with either the control arm or the intervention arm (Group 1 and Group 2, see Table 1). With an equal number of participants being in each group. A random team generator (https://www.randomlists.com/team-generator) will be used for randomisation (see Figure 1) and participants will be assigned their 'participant number' in the order of their participation in the study.

Table 1 - Order of study arms, Group 1 and Group 2

Group 1	Group 2		
Practice 1 (simple) RxConnect	Practice 1 (simple) RxConnect		
Practice 2 (complex) RxConnect	Practice 2 (complex) RxConnect		
Test scenario 1 Control	Test scenario 1 RxConnect		
Test scenario 2 Control	Test scenario 2 RxConnect		
Test scenario 3 Control	Test scenario 3 RxConnect		
Test scenario 4 RxConnect	Test scenario 4 Control		
Test scenario 5 RxConnect	Test scenario 5 Control		
Test scenario 6 RxConnect	Test scenario 6 Control		

Figure 1 Example of participants randomised into two groups

Group 1									
1 Participant 5	2 Participant 43	3 Participant 19	4 Participant 3	5 Participant 34	6 Participant 23				
7 Participant 30	8 Participant 27	9 Participant 21	10 Participant 22	11 Participant 7	12 Participant 1				
13 Participant 10	14 Participant 36	15 Participant 32	16 Participant 26	17 Participant 46	18 Participant 14				
19 Participant 33	20 Participant 31	21 Participant 29	22 Participant 15	23 Participant 47	24 Participant 11				
25 Participant 6									
Group 2									
1 Participant 12	2 Participant 28	- Destisinent OF							
		3 Participant 35	4 Participant 41	5 Participant 44	6 Participant 2				
7 Participant 40			4 Participant 4110 Participant 49						
	8 Participant 38	9 Participant 20		11 Participant 16	12 Participant 37				
13 Participant 39	8 Participant 38 14 Participant 18	9 Participant 2015 Participant 25	10 Participant 49	11 Participant 16 17 Participant 17	12 Participant 37 18 Participant 9				

Sample size

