A target of 30-50 participants is desirable for this descriptive exploratory mixed methods study. This number has been selected pragmatically to account for approximately 5 participants per day over 10 working days.

Sample size sufficient to calculate statistical significance will not be feasible, therefore a power calculation will not be required.

Data collection and management

Data collection

Data will be collected via audio-visual recording which will take place on the SimWard, Paterson Building, St Marys Hospital. A Scotia Medical Observation Training System (smots, Scotia UK, Edinburgh, UK), with two 3- axis, ceiling- mounted video cameras, and three mobile, high-definition cameras equipped with boom microphones, will be used. The cameras will be angles at the computer screen ann onto the workstation and will not take footage of participants faces. Participants will be asked to remove or cover any name badges that may identify them prior to recording commencing.

The researcher will also keep field notes to assist with later analysis of the observations and interviews. The interviews will be transcribed verbatim by the study researcher prior to thematic analysis.

Participant demographic information will be collected via a short 'demographic questionnaire' at the beginning of the user testing session. Nasa Task Load Index questionnaires will be complete by the participant after each of the intervention arms.

Data management

Physical copies of the consent forms and participant list with pseudonymised participant study numbers will be kept within a locked room with swipe card access to the floor of the department.

Audio-visual recordings of the observations and semi-structured interview (See Appendix 1 for a sample interview guide), psuedoanonymised data capture forms and interview transcripts will be stored on an encrypted hard drive and kept in a locked room with swipe card access to the floor of the department. Interview transcripts will use the participant's psuedoanonymous study code in place of their name.

Publication of study findings will not contain identifiable data, participants will be given a study code name and only referred to by their profession and speciality.

Data and all appropriate documentation will be stored for a minimum of 10 years after the completion of the study.

Duration of study

The duration of the study will be six months from the date of the first participant recruited.

Study outcome measures

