Hierarchical task analysis (HTA) will be conducted for each of scenario, a framework will be created apriori based on the anticipated task steps and previous research (9,10), however any additional steps will be added if observed during video analysis. HTA results for participants using RxConnect will be compared to their usual practise.

Qualitative interviews

Following completion of the user testing scenarios, the participant will be invited to take part in a short semi-structured interview regarding their experience of using RxConnect and other more generic questions regarding the use of digital dosing support and indication-based prescribing. (See Appendix 1 for a sample interview guide).

Statistics and data analysis

Sample size

A sample size of 30-50 participants is desirable for this descriptive exploratory mixed methods study. A sample size calculation is therefore not relevant for this study.

Statistical analysis

Categorical data (error counts) from the control arm and intervention arm will be compared using the chi-square test.

Continuous data (magnitude of error, time, task load) will be measured using Mann-Whitney test for non-parametric data.

Sub analysis will explore the effect of possible confounders will be measured using multivariate logistic regression, subject to effect size and sample size limitations.

Variables which may be accounted for include - group number, scenario number, prescribing scenario complexity, prescriber grade, prescriber speciality, control arm or intervention arm.

Hierarchical task analysis

Hierarchical task analysis will be conducted to provide an overview of the prescribing workflow for the control arm and intervention. Vulnerable process steps can be highlighted if they are associated with increased error or time taken when prescribing the scenarios, along with any feedback from participants during practice, observation or in the qualitative interview.

Thematic analysis

Thematic analysis will be conducted using data from throughout the observations and the qualitative interviews (11).

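### The plan sets out to prove or disprove that RxConnect is as safe as current aids, but a chi-square test with no effect estimate or interval cannot answer that

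*Combined protocol and SAP*

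**What the plan says.** The Introduction (section 1, RxConnect) hypothesises that the tool is "quicker, easier, and as safe to use as currently available prescribing aids" and continues: "This study aims to utilise user testing to prove or disprove the above hypothesis". The primary objective (section 2) is two-directional. It asks whether RxConnect "when compared with usual practice decreases or increases the number of prescribing errors". The Study Design paragraph (section 3) is softer again, with the aim "to explore the safety, performance, and user perceptions of utilising RxConnect".

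On size, section 3 says "A target of 30-50 participants is desirable for this descriptive exploratory mixed methods study", then "Sample size sufficient to calculate statistical significance will not be feasible, therefore a power calculation will not be required". The second Sample size paragraph, under Statistics and data analysis, adds "A sample size calculation is therefore not relevant for this study".

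The Statistical analysis paragraph compares error counts between arms with a chi-square test. It also allows a logistic regression in which arm is one of the variables that may be included. That regression is a sub-analysis of confounders and depends on effect size and sample size. Nowhere do the documents name an effect measure, a confidence interval, a significance level, a largest acceptable increase in errors, or a rule for interpreting a null result.

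**The concern.** Quicker and easier are claims of a difference, and a difference test can support them. As safe is a claim that errors are not meaningfully more frequent. A difference test that fails to reject does not support that claim, because it fails to reject both when the methods are alike and when there are too few orders to tell them apart. The protocol expects the second situation, since it says significance is out of reach at this size.

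The result most likely to be read as confirming the safety hypothesis is therefore the one that carries least information about it. Without an estimate and interval, a reader cannot see how large an increase in errors the data still allow. The Introduction says the outputs will inform development of the tool before clinical deployment, so that reading could have consequences.

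**Working it through.** **Inputs from the documents.** The target is 30 to 50 participants (section 3, Sample size). The upper end follows from the stated pace: 5 per day × 10 days = 50. No derivation is given for 30, and there is no power figure to reproduce. "Table 1 - Order of study arms, Group 1 and Group 2" shows six test scenarios per participant, three with each method. Orders per arm are therefore 30 × 3 = 90 to 50 × 3 = 150.

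**Assumptions, not in the documents.** Error rates are 10% to 40%; each scenario gives one order, scored once as correct or incorrect; orders are independent; tests are two-sided at 5%.

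**Power of the chi-square test.** For error rates p₁ and p₂ with mean p̄ and n orders per arm, power ≈ Φ[(|p₂ − p₁| − 1.96·√(2p̄(1 − p̄)/n)) / √((p₁(1 − p₁) + p₂(1 − p₂))/n)].

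For 10% v 20% at n = 90, the two standard errors are 0.0532 and 0.0527. Then (0.10 − 1.96 × 0.0532)/0.0527 ≈ −0.08, and power is 0.467.

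| True rates | Power, n = 90 | Power, n = 150 | Missed |
|---|---|---|---|
| 10% v 20% | 0.467 | 0.681 | 53% to 32% |
| 20% v 30% | 0.340 | 0.516 | 66% to 48% |
| 20% v 40% | 0.839 | 0.969 | 16% to 3% |

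A large gap would usually be found. A rise of 10 points often would not.

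**Precision with equal true rates p.** Half-width = 1.96·√(2p(1 − p)/n).
- p = 0.2: 1.96·√(0.32/90) = 0.117; 1.96·√(0.32/150) = 0.091.
- p = 0.1: 1.96·√(0.18/90) = 0.088; 1.96·√(0.18/150) = 0.068.

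**What a null result leaves open.** In a simulation with equal true rates (200,000 runs), the share of non-significant results whose upper 95% limit was +10 points or more was 61% (n = 90) and 41% (n = 150) at 20% rates. At 10% rates it was 38% and 16%.

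**A single example.** Suppose 18/90 errors with control and 27/90 with RxConnect. The uncorrected chi-square gives p = 0.12. The difference is 0.30 − 0.20 = 0.10, with standard error √(0.2 × 0.8/90 + 0.3 × 0.7/90) = 0.064. The 95% interval is −2.6 to +22.6 points. The planned test would report no significant difference and hide that interval.

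**Sensitivity to pairing.** Each participant uses both methods, so a paired analysis can be more precise. Multiplying the variance by (1 − ρ), with ρ assumed to be 0.1 to 0.3, gives half-widths at p = 0.2 of 11.1 to 9.8 points (30 participants) and 8.6 to 7.6 points (50). The interval stays wide.

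**Sensitivity to scenario count.** Step 8 of the draft session procedure (Appendix 2) mentions four scenarios, where Table 1 has six.

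| Reading of step 8 | Orders per arm | Power, 10% v 20% | Half-width at 20% |
|---|---|---|---|
| Four in total | 60 to 100 | 33% to 51% | 14.3 to 11.1 points |
| Four per arm | 120 to 200 | 58% to 80% | 10.1 to 7.8 points |

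**The case against.** The misreading is hypothetical. No section says a null result will be taken as equal safety, and the wording at issue appears only in the Introduction. The operative primary objective asks about an increase or a decrease, which a difference test does address. The study calls itself descriptive and exploratory and admits that it is under-sized, so much of the power arithmetic quantifies a limitation already conceded. The figures are also not a calculation of the protocol's own outcome. That outcome counts errors per scenario, a scenario can carry several, and the error rates are assumed.

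These points lower the weight of the concern but do not remove it. The exploratory label argues for reporting an estimate with its uncertainty, and the plan names only tests. Even for the two-directional objective, a p-value does not say how large the change in errors is. The figures are illustrations, and the conclusion does not depend on any one assumed rate. It is fair to say that the tension between the hypothesis and the two-directional objective is mild. The sharper conflict is between proving or disproving and describing. The scenario-count mismatch is a separate matter that affects only the size of the numbers here.

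**Conclusion.** The concern holds and should be fixed. As written, the plan cannot answer its own safety hypothesis: the only unconditional comparison of the primary outcome is an unpaired difference test, and nothing prevents a null from being presented as equal safety. The 95% interval would reach roughly 9 to 12 points either side of zero at a 20% error rate, and 7 to 9 points at 10%. These widths assume six scenarios as in Table 1, yes/no scoring, independent orders and the stated rates. Clustering by participant and scenario could move precision in either direction. The data remain usable; what is at risk is the headline safety conclusion.

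**What to change.** 1. In Statistical analysis (section 3), make the primary result the RxConnect-minus-control difference in errors per order, with a 95% confidence interval that respects the cross-over and the repeated orders. A simple version takes each participant's difference, averages the Group 1 and Group 2 means with equal weight, and uses a t-based interval. Under Table 1, Group 1's difference contains the effect plus the later-minus-earlier block difference, and Group 2's contains the effect minus it. Scenario set and period therefore cancel, assuming no carry-over and the same RxConnect effect in both scenario sets. State how incomplete sessions are handled.
2. In the Introduction, replace the aim of proving or disproving with one of estimating, in line with section 2.
3. Add that a non-significant result will not be reported as evidence of equal safety.
4. Replace the two sample-size statements in section 3 with the precision expected from 30 to 50 participants, once Table 1 and Appendix 2 agree on the number of scenarios.
5. Only if the team wants to keep a claim of equal safety: name and justify the largest acceptable increase before data collection, and require the upper 95% limit to lie below it. A formal non-inferiority test is not needed for an exploratory study.

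**Cost.** No extra participants or data, slightly more analysis than a chi-square, and some rewording. Section 6 reports that HRA approval has been obtained, so the change may need an amendment. The study will be able to claim less, because the interval is wide at this size.

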2. STUDY OBJECTIVES

Primary objective

To determine whether the use of RxConnect as a prescribing aid, when compared with usual practice decreases or increases the number of prescribing errors

Secondary objectives

To determine whether the use of RxConnect as a prescribing aid, when compared with usual practice-

- 1. Decreases or increases the magnitude of dose errors
- 2. Decreases or increases the time to prescribe a medication
- 3. Decreases or increases the mental load as perceived by the prescriber
- 4. Alters the prescribing workflow

To explore the opinions of the participants regarding the use of RxConnect as a prescribing aid and indication-based prescribing more generally.

3. STUDY DESIGN

Study Design

A mixed-methods cross-over observational study will be conducted to explore the safety, performance, and user perceptions of utilising RxConnect to support prescribing, in comparison to current practice.

Direct observation of participants will be conducted using multi-angle audio-visual recording, this will be set up behind the computer workstation, to capture the computer display and from above to capture the workstation. The cameras will not be angled to take footage of the participant face. A member of the research team will also be present through the study session.

Prescribing scenarios will be presented on laminated paper along with any relevant patient information, e.g. patient gender, age, weight, diagnosis, relevant medical history, relevant laboratory results.

Intervention arm: Prescribing with RxConnect via a prototype user interface

Participants will be asked to complete a number of practice prescribing tasks whilst *thinking aloud* to describe their thought process and actions. To undertake the prescribing tasks, participants will be asked to use the prototype user interface emulating an electronic prescribing front end, which presents RxConnect medication guidance to the clinical end user (the participant).

Once familiarised with the software workflow, the test prescribing tasks will be given to the participant. For these tasks the participants will be asked to perform the task without the need to think aloud. If the participant wishes to continue to think aloud so long as it doesn't distract

them from completing the task. The medication order the participants have generated using RxConnect support via the user interface will then auto populate a medication order form.

Control arm: Prescribing on Cerner with existing resources

Participants will be asked to perform similarly simple and then complex tasks using their usual practice methods when prescribing. Access will be provided to the prescribers usual electronic prescribing platform, including links to the British National Formulary, Medicines complete, local antimicrobial stewardship application, local intranet, and a generic online search engine. A hard copy of the BNF and BNFc will also be readily available.

As with the intervention arm, if the participant wishes to continue to think aloud so long as it doesn't distract them from completing the task. Participants will be asked to enter their medication order for the patient within a 'test ward' on the Cerner Millennium Powerchart system.

Order of control vs intervention arm-

Each participant will be randomly assigned to begin with either the control arm or the intervention arm (Group 1 and Group 2, see Table 1). With an equal number of participants being in each group. A random team generator (https://www.randomlists.com/team-generator) will be used for randomisation (see Figure 1) and participants will be assigned their 'participant number' in the order of their participation in the study.

Table 1 - Order of study arms, Group 1 and Group 2

Group 1	Group 2		
Practice 1 (simple) RxConnect	Practice 1 (simple) RxConnect		
Practice 2 (complex) RxConnect	Practice 2 (complex) RxConnect		
Test scenario 1 Control	Test scenario 1 RxConnect		
Test scenario 2 Control	Test scenario 2 RxConnect		
Test scenario 3 Control	Test scenario 3 RxConnect		
Test scenario 4 RxConnect	Test scenario 4 Control		
Test scenario 5 RxConnect	Test scenario 5 Control		
Test scenario 6 RxConnect	Test scenario 6 Control		

Figure 1 Example of participants randomised into two groups

Group 1									
1 Participant 5	2 Participant 43	3 Participant 19	4 Participant 3	5 Participant 34	6 Participant 23				
7 Participant 30	8 Participant 27	9 Participant 21	10 Participant 22	11 Participant 7	12 Participant 1				
13 Participant 10	14 Participant 36	15 Participant 32	16 Participant 26	17 Participant 46	18 Participant 14				
19 Participant 33	20 Participant 31	21 Participant 29	22 Participant 15	23 Participant 47	24 Participant 11				
25 Participant 6									
Group 2									
1 Participant 12	2 Participant 28	- Destisinent OF							
		3 Participant 35	4 Participant 41	5 Participant 44	6 Participant 2				
7 Participant 40			4 Participant 4110 Participant 49						
	8 Participant 38	9 Participant 20		11 Participant 16	12 Participant 37				
13 Participant 39	8 Participant 38 14 Participant 18	9 Participant 2015 Participant 25	10 Participant 49	11 Participant 16 17 Participant 17	12 Participant 37 18 Participant 9				

Sample size

A target of 30-50 participants is desirable for this descriptive exploratory mixed methods study. This number has been selected pragmatically to account for approximately 5 participants per day over 10 working days.

Sample size sufficient to calculate statistical significance will not be feasible, therefore a power calculation will not be required.

Data collection and management

Data collection

Data will be collected via audio-visual recording which will take place on the SimWard, Paterson Building, St Marys Hospital. A Scotia Medical Observation Training System (smots, Scotia UK, Edinburgh, UK), with two 3- axis, ceiling- mounted video cameras, and three mobile, high-definition cameras equipped with boom microphones, will be used. The cameras will be angles at the computer screen ann onto the workstation and will not take footage of participants faces. Participants will be asked to remove or cover any name badges that may identify them prior to recording commencing.

The researcher will also keep field notes to assist with later analysis of the observations and interviews. The interviews will be transcribed verbatim by the study researcher prior to thematic analysis.

Participant demographic information will be collected via a short 'demographic questionnaire' at the beginning of the user testing session. Nasa Task Load Index questionnaires will be complete by the participant after each of the intervention arms.

Data management

Physical copies of the consent forms and participant list with pseudonymised participant study numbers will be kept within a locked room with swipe card access to the floor of the department.

Audio-visual recordings of the observations and semi-structured interview (See Appendix 1 for a sample interview guide), psuedoanonymised data capture forms and interview transcripts will be stored on an encrypted hard drive and kept in a locked room with swipe card access to the floor of the department. Interview transcripts will use the participant's psuedoanonymous study code in place of their name.

Publication of study findings will not contain identifiable data, participants will be given a study code name and only referred to by their profession and speciality.

Data and all appropriate documentation will be stored for a minimum of 10 years after the completion of the study.

Duration of study

The duration of the study will be six months from the date of the first participant recruited.

Study outcome measures

The following outcomes will be measured-

Primary outcome measure-

Number of prescribing errors per scenario

• Subcategorised as - Incorrect drug, dose, route, frequency or patient.

Secondary outcome measures-

- The magnitude of any dose errors (deviation from recommended dosing range)
- Time taken to prescribe each medication
- Prescribers perceived mental load per prescribing scenario
- Hierarchical task analysis
- Qualitative feedback from participants

Number and magnitude of prescribing errors

We define a prescribing error as any of the following errors:

- Incorrect prescribed dose: prescribed doses that deviate from the recommended dose in the BNF/ BNFc or local guideline by more than 10%.
 - If the recommended dose is a range, deviations will be calculated from the max/min
 of the range, whichever is closest to the user calculated dose. If there are multiple
 recommended dose options e.g., from the BNF and from local guidelines, the
 researcher will calculate deviations based on the most appropriate source for the
 indication. When all sources are deemed equally valid, the researcher will record
 the smallest deviation allowed.
 - Magnitude of dosing error will be calculated as a percentage deviation from the recommended dose.
- Incorrect prescribed route: a medication prescribed via a route that deviates from the recommended route for the medication and dose as per the BNF/BNFc or local guidelines.
- Incorrect prescribed frequency: a medication prescribed for a frequency that deviates from the recommended frequency or that accumulated to a total daily dose for the medication and dose as per the BNF/BNFc or local guidelines.
- Incorrect patient: a medication order issued to incorrect patient's electronic medication chart.

Time

The length of time for each prescribing scenario will be calculated from the time the participant begins to read the first scenario, and for subsequent scenarios from the time they complete one scenario and move onto the next.

Task load index

At the end of each scenario the user will be provided with an online NASA TLX (task load index) form to complete (8).

Hierarchical task analysis

Hierarchical task analysis (HTA) will be conducted for each of scenario, a framework will be created apriori based on the anticipated task steps and previous research (9,10), however any additional steps will be added if observed during video analysis. HTA results for participants using RxConnect will be compared to their usual practise.

Qualitative interviews

Following completion of the user testing scenarios, the participant will be invited to take part in a short semi-structured interview regarding their experience of using RxConnect and other more generic questions regarding the use of digital dosing support and indication-based prescribing. (See Appendix 1 for a sample interview guide).

Statistics and data analysis

Sample size

A sample size of 30-50 participants is desirable for this descriptive exploratory mixed methods study. A sample size calculation is therefore not relevant for this study.

Statistical analysis

Categorical data (error counts) from the control arm and intervention arm will be compared using the chi-square test.

Continuous data (magnitude of error, time, task load) will be measured using Mann-Whitney test for non-parametric data.

Sub analysis will explore the effect of possible confounders will be measured using multivariate logistic regression, subject to effect size and sample size limitations.

Variables which may be accounted for include - group number, scenario number, prescribing scenario complexity, prescriber grade, prescriber speciality, control arm or intervention arm.

Hierarchical task analysis

Hierarchical task analysis will be conducted to provide an overview of the prescribing workflow for the control arm and intervention. Vulnerable process steps can be highlighted if they are associated with increased error or time taken when prescribing the scenarios, along with any feedback from participants during practice, observation or in the qualitative interview.

Thematic analysis

Thematic analysis will be conducted using data from throughout the observations and the qualitative interviews (11).

